## F. ADVERSE EVENTS OR EFFECTS

1. Who will handle adverse events?  Investigator  Referral  Other, explain:

N/A

2. Are your facilities and equipment adequate to handle possible adverse events?  Yes  No, explain:

A first aid kit will be available, if needed, to address minor injuries (e.g., scrapes or minor cuts). The investigators will contact emergency services (911) if a serious adverse event occurs. The UW Medical Center emergency room is located 5 floors below the researchers' laboratory.

## G. CONFIDENTIALITY OF RESEARCH DATA

1. Will you record any direct subject identifiers (names, Social Security numbers, patient, hospital, laboratory or claim numbers, addresses, telephone numbers, locator information, etc.)  No  Yes If yes, explain why this is necessary and describe the coding system you will use to protect against disclosure.

Subject identifiers will be recorded (name, telephone number, social security number). Name and contact information are needed to schedule participant data collection sessions. Social security information is required by UW when payments of more than \$50 are made to study subjects. Identifying information will be linked to a 5-digit numeric study code. The file containing identifying information and the linked subject code will be stored separately from all other study data in a secure and password protected computer only accessible to study researchers.

2. Will you retain a link between study code numbers and direct identifiers after the data collection is complete?  No  Yes If yes, explain why this is necessary and for how long you will keep this link.

This research is a pilot study in a new line of investigation for our research lab (i.e., same PI and research team). We are currently pursuing funding for parallel studies of prosthetic foot technologies. We wish to combine data from related studies to maximize our ability to recruit from the small local population of people with lower limb loss. Combining data from multiple studies would increase our power to detect differences and avoid participation of individuals in both studies (participation in both studies would lead to including a participant's data twice in the same dataset). To allow for accurate longitudinal tracking of participants, we will retain the link between identifiers and study code numbers until 2026. Participants may request that we destroy their link at any point during the study, or any time thereafter.

3. Describe how you will protect data against disclosure to the public or to other researchers or non-researchers. Explain who (other than members of the research team) will have access to data (e.g., sponsors, advisers, government agencies, etc.).

Data will be stored on a study specific password protected computer which will be stored in a locked cabinet in the PI's office. Only members of the research team will have access to the information.

4. Will you place a copy of the consent form or other study information in the subject's medical or other personal record?  No  Yes. If yes, explain why this is necessary.

N/A

5. Do you anticipate using any data (information, specimens, etc.) from this study for other studies in the future?  No  Yes If "Yes," explain and include this information in the consent form.

As noted above, this research is a pilot study in a new line of investigation for our research lab. We are currently pursuing funding for similar (parallel) studies of the prosthetic foot technologies included in this study. To maximize available resources and address larger research questions, we will combine data from this study with data obtained in subsequent studies. We have added this information to the consent form.

#### H. ADDITIONAL INFORMATION

1. If the study will involve radiation exposure to subjects, e.g., X-rays, radioisotopes, what is status of review by the UW Radiation Safety Committee (RSC):  Pending  Approved (Attach one copy of approval.)  NA

2. Does this research require approval from the UW Institutional Biosafety Committee (IBC) for recombinant/synthetic DNA human Gene transfer or vaccines?

No  Yes. If yes, what is the status of review by IBC?  Pending  Approved (Attach one copy of approval.)  NA

3. Protected Health Information (PHI). Will you or any member of your research team obtain, access, or use a subject's protected health information by any method, and for any purpose including "pre-screening"?

*"Methods" may include but are not limited to: directly looking at a medical record (electronic or paper), requesting medical record information from a service such as the UW Center for Health Excellence, or viewing surgery schedules, clinic records, appointment books, etc.*

*Examples of where PHI may be located include: medical records, dental records, clinical lab tests that you will have performed on subject samples, pharmacy records, medical billing records, clinical databases, etc.*

No  Yes. If "yes":

a. Describe the type of records/data, location and how you will obtain the information:

We will collect information on the participants' prostheses, including delivery schedule, components, and problems experienced by the participants (related to fit and function of their prostheses) while they are part of the study. Information will be collected directly from the participant's practitioner ([name]). Participants will be asked to complete a HIPAA authorization to allow us to collection information about their prosthesis directly from their practitioner (**Appendix 6**).

b. Will you obtain any of the information without HIPAA authorization from each subject?

No  Yes. If "yes": Complete and attach the SUPPLEMENT: Waiver Request, HIPAA Authorization, and the SUPPLEMENT: Waiver Request, Consent Requirements. If the records are owned by the University of Washington or a state agency, complete and attach a UW Confidentiality Agreement.

c. Will you obtain HIPAA authorization from subjects for any of the information?

No  Yes. If "yes", attach the HIPAA Authorization form you propose to use  
See attachment (**Appendix 6**).

d. Will you be obtaining any of the data as a Limited Data Set?

No  Yes

4. Other Records. Will you or any member of your research team obtain, access, or use academic, employment, or any other type of records about subjects, by any method, and for any purpose including "pre-screening"?

*"Methods" may include but are not limited to: directly looking at a record (electronic or paper), requesting records from offices such as Payroll or the UW Registrar's Office, obtaining records from the state Department of Health, etc.*

No  Yes. If "yes":

a. Describe the type of records/data, location, and how you will obtain the information.

N/A

b. Will you obtain any of the information without the subject's consent?

No  Yes.

If the records are owned by the University of Washington, complete and attach a UW Confidentiality Agreement.

5. Will you use the Clinical Research Center (CRC) at the UW or Seattle Children's for any of your research activities?

No  Yes.

If you answered "yes":

A medical record will be created for your subjects at UW Medicine and CRC staff may need to access those medical records for you. This may be because they are performing procedures or collecting data for you. It may also be required if an event happens on the CRC that requires treatment (such as fainting during a blood draw). This means that you must obtain a signed HIPAA Authorization form from each subject and give a copy of it to the CRC. Complete and attach the UW research HIPAA Authorization template, available on the HSD Forms webpage. There is guidance in the template about how to describe the information that the CRC staff may access and disclose to you.

6. Does your research involve any of the following:

- Students age 21 or younger who may be participants in your research?
- Access to, or use of, personally identifiable information from student (current or past) education records from any institution or agency of education (including, but not limited to, pre-elementary, secondary, post-secondary, job training, adult education, career and technical education, special education)?
- Conducting any research procedures in an educational setting?

No  Yes.

If you answered "yes":

Your research may be subject to the requirements of the **Protection of Pupil Rights Amendment (PPRA)** and/or the **Family Education Rights and Privacy Act (FERPA)**.

Consult with the SOP Research Involving Students to determine whether PPRA or FERPA regulations apply to your research.

Check the appropriate box.

- PPRA regulations apply to my research
- FERPA regulations apply to my research
- Both PPRA and FERPA regulations apply to my research
- Neither set of regulations apply to my research

7. Will you make audio-visual or tape recordings or photographs of subjects?  No  Yes. If yes, explain what type of recordings you will make, how long you will keep them, and if anyone other than the members of the research team will be able to see them.

With participant's consent, we will take video and/or photographs of study procedures for use in grant applications, presentations, or publications (**Appendix 7**). Consent for photos/videos is not required to participate in the study. We will not destroy photos and/or videos.

8. Will your study involve use of equipment involving energy input to the subjects (EMG, EKG, MRI, ultrasound, etc.)?  No  Yes. If yes, attach documentation that all equipment will be tested regularly by the Scientific Instrument Division (call [contact] for information) or describe safety testing procedures you will use.

N/A

9. Confirm by checking the box that the principal investigator on this IRB application has ensured that all investigators (as defined by UW policy GIM 10) are aware of policy GIM 10 and their responsibility for complying with its relevant requirements.

Confirmed

10. Does the individual who is the principal investigator on (1) this IRB application or (2) any grants or contracts supporting this research have a financial conflict of interest with respect to this research?  No  Yes.

If yes, has it been disclosed to the University? (Since August 24, 2012, all disclosures are made through the University's online Financial Interest Disclosure System.) Final review of this application cannot occur until the disclosure has been made and reviewed by the University, and the outcome has been incorporated into the IRB's review.  No  Yes  Not applicable, because there is no financial conflict of interest.

11. Is your research:

- Clinical research that will bill subjects or their health insurance for UW Medicine professional or facility services, items, or tests\*, AND/OR
- An "applicable clinical trial" as defined below" \*\*

No  Yes

If you selected "yes", you must register your research at the federal site ClinicalTrials.gov

See the HSD document titled: ClinicalTrials.gov – Instructions for Registering Your Trials for step-by-step instructions about how to register your research.

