Commercially-available running-specific feet (RSF) like the Össur Cheetah (Össur, Reykjavik, Iceland) allow people with LLA to participate in athletic activities and sporting events. RSF provide significantly enhanced performance, compared to traditional ESF, by extending the length and increasing the stiffness of the prosthetic keel (forefoot). RSF also do not include a heel, as they are used only for running activities. Although transtibial runners with RSF exhibit endurance levels similar to non-amputees, the RSF design does not allow the biomechanical movements or provide the stability needed to use the foot for walking (over level or uneven terrain).

A Seattle-area prosthetist, [name], currently provides many of his active LLA patients with a modified running-specific foot (mRSF). The mRSF combines the running keel (forefoot) of a RSF with the walking heel of a ESF. The mRSF can then be used for walking, running, and other routine daily activities. [name] has fit and provided this prosthetic foot on over 100 of his patients. Preliminary feedback suggests that users experience improved overall function and high satisfaction with the device. However, empirical evidence is needed to support prescription of this prosthetic foot at other clinical facilities. The goal of this study is therefore to evaluate endurance, walking performance, mobility, and perceived exertion of transtibial prosthesis users (i.e., study participants) walking with a conventional ESF and the mRSF. Results will be compared to determine if the mRSF provides superior performance to the ESF, which is commonly prescribed to most active individuals with LLA.

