**B. RESEARCH PROCEDURES INVOLVED.**

1. Provide a complete description of: a. the study design, and b. sequence and timing of all study procedures that will be performed, e.g., volume of blood, size of biopsy, drug administration, questionnaire, name of psychological test. Provide this information for each phase of the study (pilot, screening, intervention and follow-up). **Use lay language.** Attach study flow sheet, if available.

We will conduct a study to compare endurance, walking performance, mobility, and perceived exertion of participants with transtibial amputation wearing two different prostheses: (1) a prosthesis with a modified Running Specific Foot (mRSF), and (2) a prosthesis with a Energy Storing Foot (ESF). To maximize study resources, we will recruit participants who will be receiving from their prosthetist the mRSF prosthesis as part of their normal clinical care. We will fabricate a duplicate prosthesis with the ESF as part of this study to be used as a comparison.

*Note: Both the mRSF and ESF included in this study are devices that people with LLA use daily in their normal lives outside of this study. These feet (and other components included in the prostheses created for this study) are class I devices and exempt from U.S. Food and Drug Administration premarket notification procedures.*

We will conduct a randomized crossover study to compare endurance, energy expenditure, and reported health of participants with transtibial amputation wearing prostheses with the mRSF and ESF described above. Study participants will be randomly assigned to the first foot condition (i.e. ESF or mRSF). To standardize test conditions, the participant's prosthetist ([name]) will fabricate two comparable prostheses with identical (i.e. duplicated) prosthetic sockets, interfaces, and suspension mechanisms. The same socket cannot be used for both prostheses because of the unique, direct-lamination attachment of the mRSF to the socket. The duplicate socket will be fitted with common ESF, the Ossur Vari-flex foot. We have obtained written commitments from Ossur to donate prosthetic components and from Davidson Prosthetics to donate time and materials needed to fabricate the duplicate sockets and test prostheses. Participants will be asked to wear the same athletic shoes for all sessions in order to standardized footwear between tests.

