Session 2: The second session will be performed after participants use the randomly-assigned ESF or mRSF prosthesis for a period of 1 month. Upon arrival at the lab, study

staff will remove the activity monitor and ask the participant to complete a self-report survey (**Appendix 2**) to evaluate their perceived performance, health, and satisfaction with their prosthesis. The survey will be administered on a tablet computer (iPad) and includes the following standardized instruments selected to measure participants' mobility, fatigue, balance confidence, activity restrictions, and satisfaction:

- Prosthetic Limb Users Survey of Mobility - PLUS-M measures respondents' self-reported mobility with a prosthesis. The PLUS-M was developed by the investigators in a prior study to address methodological limitations present in existing mobility measures. We will administer the PLUS-M computer adaptive test (CAT) to achieve the greatest precision of measurement and ease respondents' burden (i.e., CAT requires participants answer fewer questions than would taking the entire survey).
- PROMIS - Fatigue - PROMIS-F measures symptoms and effects of fatigue on respondents' ability to execute daily activities over a 1-week recall period. We will also administer PROMIS-F by CAT.
- Activities Specific Balance Confidence Scale - ABC measures respondents' confidence in performing basic ambulatory activities. We will administer a version of the ABC recommended to ease administration and improve scoring. All 16 questions of the ABC will be administered (CAT not available).
- Trinity Amputation and Prosthesis Experience Scales - Revised - TAPES-R is a multidimensional health instrument that measures activity restrictions and satisfaction with a prosthesis. We will administer 19 TAPES-R questions (CAT not available).

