## E. RISKS AND BENEFITS

In order to approve the research the IRB must find that risks are reasonable in relation to anticipated benefits, if any, to subjects, and the importance of the knowledge that may reasonably be expected to result.

1. Describe nature and degree of risk of possible injury, stress, discomfort, invasion of privacy, and other side effects from all study procedures, drugs and devices (standard and experimental), interviews and questionnaires. Include psycho-social risks as well as physiological risks. Include risks of withholding standard care or procedures if this is the case. Do not reference the consent form.

Participants will be asked to walk for about 70 minutes total for this study (a maximum of 6 minutes at a time, and 30 minutes maximum per session). Because they are being asked to walk, there is the risk that they could become fatigued during the study procedures. In addition, there is a risk of falling. However, these risks are no larger than the risks that study participants generally undertake when walking outside of this study.

2. Explain what steps you will take to minimize risks of harm and to protect subjects' rights and welfare. (If you will include protected groups of subjects (minors; fetuses in utero; prisoners; pregnant women; unviable neonates; neonates of uncertain viability; decisionally impaired or economically or educationally disadvantaged subjects) please identify the group(s) and answer this question for each group. Please also complete the SUPPLEMENT: Protected and/or Vulnerable Populations.)

This study will not require participants to perform activities at a level of endurance that they would not typically do outside of the study session. To minimize risks of fatigue and falling during the study session, the participants will be asked to take breaks after each walking measure is collected. The maximum time that each participant will be asked to walk continuously is 6 minutes. They are also instructed to take a break, including a sitting break, at any time during the data collection session, including in the middle of walking measures. If at any time it appears that the participant is at risk of falling or other harm, the data collection session will be stopped.

3. Is it possible that you will discover a subject's previously unknown condition (disease, suicidal intentions, genetic predisposition, etc.) as a result of study procedures?  No  Yes If yes, explain how you will handle this situation.

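### Fit and function problems in the two home months are taken from the prosthetist who makes both limbs; the text shown has no question to participants about them or about falls

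*Protocol*

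**What the plan says.** Section VIII.H.3 (Protected Health Information) lists what the study will obtain about the prostheses: delivery schedule, components and "problems experienced by the participants (related to fit and function of their prostheses) while they are part of the study". It then names the source: "Information will be collected directly from the participant's practitioner".

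The same practitioner appears elsewhere in the protocol. Section VIII.A says he has fitted the mRSF on more than 100 of his patients and reports that "Preliminary feedback suggests that users experience improved overall function and high satisfaction with the device". Section VIII.B.1 says he "will fabricate two comparable prostheses with identical (i.e. duplicated) prosthetic sockets, interfaces, and suspension mechanisms", and that his practice donates time and materials. The mRSF reaches participants by ordinary care, since the study enrols people who will be "receiving from their prosthetist the mRSF prosthesis as part of their normal clinical care". The energy storing foot (ESF) limb is a duplicate made for the study.

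Each foot is worn for 1 month before its test session. At Sessions 2 and 3 participants complete a tablet survey that includes PLUS-M, PROMIS-Fatigue, ABC and 19 TAPES-R questions, described as "standardized instruments selected to measure participants' mobility, fatigue, balance confidence, activity restrictions, and satisfaction". Section VIII.E.1 states: "In addition, there is a risk of falling". Section VIII.F.2 describes a first aid kit, calling emergency services and a nearby emergency room.

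**The concern.** A fit problem reaches the data by the described route only if the participant takes it to the prosthetist and he passes it on. He cannot be blind to the foot, and he has an existing commitment to one of the two. Contact with his clinic may also differ by foot, because one limb is the patient's own care and the other is a study duplicate. Falls at home are less likely still to arrive this way: they are not obviously fit or function problems, and a participant may see no reason to report one to a prosthetist.

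What is at stake is the tolerability side of the comparison. Section VIII.A asks whether the mRSF performs better than the ESF and says evidence is needed to support its prescription at other facilities. Section VIII.E.5 gives wider availability as the benefit to society. A favourable result on walking and self-report would be read for that purpose, and a reader would want to know how each foot was tolerated over its month of daily use.

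**Working it through.** The protocol states no problem rate, fall rate or reporting rate, so there is no figure to reproduce and the size of any under-recording cannot be calculated. The check is a reading of every place that could supply home-month events.

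1. **Exposure.** The approved number of subjects is 24 and each foot is worn for 1 month. That is at most 24 × 1 = 24 person-months per foot, or 24 × 2 = 48 in all, assuming everyone completes both periods.
2. **Practitioner record (VIII.H.3).** It covers fit and function problems. Falls and other events unrelated to the prosthesis are not named.
3. **Participant survey (VIII.B.1, Session 2, repeated at Session 3).** The constructs are mobility, fatigue, balance confidence, activity restriction and satisfaction. ABC asks about confidence, not about falls that occurred. No item on falls, skin, pain, repairs or non-wear is described.
4. **Step activity monitor (VIII.B.1, Session 1).** It counts steps away from the laboratory and comes off at Session 2. Days with no steps would point to non-wear, but not to the reason. Session 3 is said to be identical, which implies wear in the second month too, although handing the monitor over to the second limb is not spelled out.
5. **Risk section (VIII.E.1 and E.2).** Fatigue and falling are discussed for walking in the sessions, with breaks and stopping rules for those sessions.
6. **Adverse events (VIII.F).** The surviving text concerns facilities to respond to an injury. It does not describe asking about events between visits.
7. **Hypotheses (VIII.A).** 1a, 1b, 2a and 3a concern walking distance, perceived exertion, reported mobility, balance confidence, health and fatigue, and net energy cost. None draws on the practitioner's record.

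Steps 2 to 6 show one stated source for fit problems, which is not independent of the mRSF, and none described for falls at home. Step 7 shows that this does not enter a planned comparison.

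**The case against.** The strongest reply is that section VIII.H.3 answers a question about protected health information. It says what comes from the practitioner and does not say he is the only source. The survey itself is Appendix 2, which is not shown, and the protocol says only that it includes the listed instruments, so fall or skin items may already be there. The check mark for who handles adverse events (VIII.F.1) cannot be read. All of this stands, and it makes the point conditional on Appendix 2.

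It is also fair that ABC and TAPES-R are completed in the same way for both feet, so a troublesome foot would be partly visible, and that this is a minimal-risk pilot of class I devices already in daily use.

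A reader might infer several stronger things that the protocol does not support:

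- **That the practitioner recruits the patients.** Section VIII.D.7 says he only informs them; study staff do the recruitment and enrolment.
- **That the protocol itself makes falls the main drawback of the mRSF.** The remark in VIII.A about lacking stability for walking concerns the unmodified, heel-less running foot. The mRSF adds a walking heel.
- **That recording is known to differ by foot.** The same person makes both limbs with duplicated sockets. Unequal recording is a possibility that follows from his knowledge and position, and nothing shown demonstrates it.
- **That the site table contradicts VIII.H.3 by marking the practice as not applicable for data collection.** Investigators obtaining information from the practitioner is compatible with that entry.

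**Conclusion.** The point holds as a gap in tolerability information. On the text shown, fit and function problems come from an unblinded practitioner with a commitment to the mRSF, and participants are not described as being asked about those problems or about falls over at most 24 person-months per foot. Under-recording can occur, and could differ by foot; neither its size nor its direction can be derived from the protocol.

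A reader might go on to conclude that the trial's main results are biased. That does not follow, because no stated hypothesis uses the problem record. The consequence is narrower: a result favouring the mRSF would come without comparable tolerability data for the two feet. The verdict assumes that Appendix 2 and the other unseen attachments do not already contain such questions. The change is a worthwhile, inexpensive improvement, not a correction to a planned analysis.

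**What to change.** First check Appendix 2. If the items are there, naming them in the Session 2 description in VIII.B.1 is enough.

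If not, add three or four fixed questions to the tablet survey at Sessions 2 and 3, worded identically for both feet and referring to the past month with the assigned prosthesis:

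- number of falls;
- any skin breakdown or pain from the prosthesis;
- days not worn, and why;
- unscheduled adjustments.

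Tabulate the answers descriptively by foot, without testing. Use the step monitor to cross-check reported non-wear. Keep the practitioner's record as a secondary source, and say in VIII.H.3 that it is one.

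The cost is about 2 minutes per session, so about 2 × 2 = 4 minutes per participant against two sessions of about 3 hours each, plus a small survey revision and an IRB modification. No extra visit or staff is needed.
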